### 6.2.3 Prohibited Concomitant Therapy

During the course of the study, patients may not receive other additional investigational drugs, agents, devices, anti-neoplastic therapy, or any other therapies that may be active against cancer. Additionally, no other therapeutic monoclonal antibodies and no immunosuppressive medication may be administered while on this study. [REDACTED]

[REDACTED]

[REDACTED]

## 6.3 Patient Numbering and Treatment Assignment

### 6.3.1 Patient Numbering

Each patient is identified in the study by a number that is assigned when the patient is first enrolled for Screening. The patient number is retained as the primary identifier for the patient throughout participation in the trial. The patient number consists of the center number assigned by the Sponsor and a sequential patient number suffix so that each patient is numbered uniquely across the entire database. Patient numbers will be assigned by the Sponsor at the time of Screening.

The subject number, patient ID along, with the last IMCgp100 dose and date of last dose from the parent study will be captured in the relevant eCRF for the rollover study.

### 6.3.2 Treatment Assignment

Patients enrolled in the rollover study will be assigned to the dosing regimen (please refer to [Table 6-1, Section 6.1](#) Study Treatment) based upon the parent protocol in which the patient was enrolled and treated.

## 6.4 Study Drug Preparation and Dispensation

Further instructions for the preparation and dispensation of IMCgp100 are described in the Study Pharmacy Manual. See [Section 6.1](#) Study Treatment for details.

All dosages prescribed to the patient and all dose changes during the study must be recorded on the Dosage Administration Record eCRF.

#### 6.4.1 Packaging and Labeling of Study Drug(s)

Further instructions for the preparation and dispensation of IMCgp100 are described in the Study Pharmacy Manual. See [Section 6.1](#) Study Treatment for details.

All dosages prescribed to the patient and all dose changes during the study must be recorded on the Dosage Administration Record eCRF.

#### 6.4.2 Study Drug Compliance and Accountability

Study treatment will be administered to the patient by the trained study site staff at the study sites. Compliance with the prescribed regimen will be assured by administration of the study treatment under the supervision of investigator or his/her designee.

The investigator or designee must maintain an accurate record of the shipment and dispensing of study treatment according to local institutional drug accountability processes. Drug accountability will be noted by the field monitor during site visits and at the completion of the study. At study close-out, and, as appropriate during the course of the study, the investigator will return all used and unused study treatment, packaging, drug labels, and a copy of the completed drug accountability log to the site study monitor.

#### 6.4.3 Drug Supply, Storage, and Disposal

Study treatments must be received by designated personnel at the study site, handled and stored safely and properly, and kept in a secured location to which only the investigator and designated site personnel have access. Upon receipt, IMCgp100 supply should be recorded and stored according to the instructions specified on the drug labels.

All IMCgp100 supply remaining at the end of the study, following appropriate drug accountability procedures at each site can be destroyed per local institutional practice at the study site or at a third party vendor as appropriate and agreed with Sponsor. Used vials can be discarded according to local procedures and recorded in the accountability log. Unused vials (after expiry or at the end of study) must be disposed of only after agreement from Sponsor and a certificate of destruction must be retained within the pharmacy binder.

### 6.5 Management and Follow-up of Toxicity

Patients whose study treatment is interrupted or permanently discontinued due to an AE or clinically significant laboratory value, must be followed-up at least once a week (or more if clinically indicated) for 4 weeks, and subsequently at approximately 4-week intervals, until resolution or stabilization of the event, whichever comes first. Appropriate clinical experts should be consulted as deemed necessary for any AEs

observed in the course of the trial. In the case of a toxicity suspected to be related to a cytokine release syndrome, the immunologic assessments outlined in [Section 7.3.4](#) should be performed.

Guidelines for management of AE and dose modifications are presented below in [Table 6-2](#) (below). Institutional protocols for management of immune-related AEs should be implemented in cases of immune-related AEs and will take precedence over guidance in [Table 6-2](#). All patients must be followed up for the occurrence of AEs and SAEs for 90 days following the last dose of IMCgp100.

**Table 6-2 Recommended Dose Modifications by Toxicity Grade for Study Medications**

Worst Toxicity NCI CTCAE v4.03 Grade	Recommended Dose Modifications
Skin Toxicity	
Rash/Photosensitivity	
Grade 1	Continue dosing. If symptomatic, consider systemic antihistamine regimen
Grade 2	Hold all doses of study IMCgp100 until returned to NCI CTCAE grade $\leq$ 1. Use local skin management and systemic antihistamine regimen as indicated. Anti-pruritic regimen: Can include antihistamine therapy. In patients where antihistamine therapy does not provide adequate relief, gabapentin or aprepitant may be considered. Topical corticosteroid regimens: Preparation of recommended regimens 
 
• For face and/or intertriginous areas (including genitalia) recommend alclometasone 0.05% or hydrocortisone 2.5% creams
 
• For other body areas (ie, trunk and extremities) recommend clobetasol or betamethasone 0.05% creams. Consider spray preparation for ease of application on trunk. For scalp involvement, consider a foam preparation
 

Grade 3	Hold all doses of IMCgp100 until returned to NCI CTCAE grade $\leq$ 1.

**Table 6-2 Recommended Dose Modifications by Toxicity Grade for Study Medications**

Worst Toxicity NCI CTCAE v4.03 Grade	Recommended Dose Modifications
	
Management: Treat according to institutional practice which generally includes an anti-pruritic regimen (see grade 2 management above). In addition, corticosteroid treatment (oral or topical) can be considered for symptomatic rash that does not respond to anti-pruritic regimen. For topical regimens, refer to grade 2 management above).
 
Dose adjustments: If grade 3 rash observed with IMCgp100 resolves to NCI CTCAE grade <math>\leq 1</math> within 7 days, restart at the same dose. If grade 3 rash resolves to NCI CTCAE grade <math>\leq 1</math> in 7–21 days, restart with a reduction in the dose of IMCgp100, as discussed with the medical monitor.

Grade 4	
Any grade 4 rash, permanently discontinue IMCgp100.
 
Manage according to institutional practice, consultation with a dermatologist is recommended.
 
All study medications must be permanently discontinued.

Infusion Reactions	
Grade 1	
Administer medications for symptomatic relief as needed. Infusion interruption may be considered until resolution of the event (up to 4 hours). The infusion rate of the study medication may be decreased by 50%. If resolved with decreased rate of infusion, any subsequent infusions can be administered at the reduced rate.

Grade 2	
Stop infusion and keep intravenous line open. Treat according to institutional practice. Provide all supportive measures as indicated. Provide supplemental oxygen and fluids, as needed.
 
Monitor vital signs (eg, blood pressure, pulse, and temperature) until resolution. Administer medications for symptomatic relief as needed. Antihistamines, acetaminophen (paracetamol), or corticosteroids may be administered, as needed at the discretion of the investigator.
 
Restart infusion only once infusion reaction resolves (within 4 hours of initial start of infusion). Administer oral pre-medication (eg, 1000 mg of acetaminophen or paracetamol, 50–100 mg diphenhydramine hydrochloride or alternative antihistamine), within 60 minutes of restarting the infusion.
 
Restart infusion at 50% of previous rate under continuous observation. Ensure that there is a minimum observation period of 1 hour prior to restarting the infusion. If the adverse event recurs at the reinitiated slow rate of infusion, and despite oral pre-medication, then permanently discontinue the patient from study treatment.

Grade 3 or 4	
Discontinue infusion immediately, and permanently discontinue patient from study treatment.
 
Manage severe infusion-related reactions per institutional standards. Provide supplemental oxygen, fluids, and other resuscitative measures as needed. Monitor vital signs (eg, blood pressure, pulse, respiration, and temperature) until resolution.

Hypotension	

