### 6.2.2 Permitted Concomitant Therapy Requiring Caution

Anti-coagulant therapy is permitted if the patients are already at stable doses of warfarin or stable doses of low molecular weight heparin for > 2 weeks at time of first dose. International normalized ratio should be monitored as clinically indicated per investigator's discretion.

Anti-hypertensives are allowed as concomitant medications; however, because transient hypotension has previously occurred during infusions of IMCgp100 and monoclonal antibodies, [REDACTED]

[REDACTED]

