**Table 6-2 Recommended Dose Modifications by Toxicity Grade for Study Medications**

Worst Toxicity NCI CTCAE v4.03 Grade	Recommended Dose Modifications
Grade 2	Intravenous fluid support and other supportive measures for additional AE as needed.
Grade 3 or 4	Hold all doses of IMCgp100 until returned to NCI CTCAE grade $\leq$ 1. Intravenous fluid support and other supportive measures for additional adverse events. In cases of hypotension where fluid support is not adequate, consider systemic corticosteroid therapy as needed for hypotension. In case of hypotension not responding to intravenous corticosteroid, inotropic pressor support may be indicated.
Cytokine Release Syndrome	
Grade 2	Interrupt infusion of IMCgp100. Supportive measures for symptoms of cytokine release, ie, intravenous fluid support, non-steroidal anti-inflammatory drug (NSAID), antihistamine. If resolves within 4 hours, may restart infusion of IMCgp100. If recurs with restarting infusion, hold the dose of IMCgp100 and institute supportive measures as indicated.
Grade 3	Discontinue infusion immediately. Supportive measures for symptoms of cytokine release, ie, intravenous fluid support, NSAID, antihistamine. To consider intravenous corticosteroid (eg, methylprednisolone or hydrocortisone) for severe symptoms and management of sequelae. If symptoms resolve to NCI CTCAE grade 1 within 7 days, may consider restarting IMCgp100 after written approval of Sponsor Medical Monitor.
Grade 4	Discontinue infusion immediately. Supportive measures for symptoms of cytokine release. In addition to supportive measures, intravenous corticosteroid dosing (eg, methylprednisolone or hydrocortisone) should be administered. If symptoms do not resolve with intravenous corticosteroid dosing consider anti-IL6 (tocilizumab) therapy. If symptoms resolve to NCI CTCAE grade 1 within 7 days, may consider restarting IMCgp100 after written approval of Sponsor Medical Monitor.
Other Adverse Events	
In patients experiencing adverse events (not meeting the specific criteria above) of grade $\geq$ 3, study drugs should be omitted until resolved to grade $\leq$ 1. Treat according to institutional practice and for immune-related adverse events of grade 3 or greater, treatment with corticosteroids should be considered. Consult Sponsor Medical Monitor for further guidance as needed.	

NCI CTCAE = National Cancer Institute Common Terminology Criteria for Adverse Events; NSAID = non-steroidal anti-inflammatory drug.

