### 7.3.2 Vital Signs

Vital signs (body temperature, pulse rate, respiratory rate, and blood pressure) must be performed before dosing, and after the IMCgp100 administration (at least twice after administration) as indicated in [Table 7-1](#), and as per institutional standards. Clinically significant abnormalities are to be reported on the AE eCRF page.

Vital signs should be assessed on the scheduled day, even if study treatment is being withheld. More frequent examinations may be performed at the discretion of the investigator if medically indicated.

Frequent vital signs, as per institutional standard, should be implemented during any inpatient observations at a minimum of every 4 hours. If the full 21-day screening period is utilized for a patient, and the patient has a gap of greater than 21 days between their last dose of IMCgp100 on the parent study, and the first dose of IMCgp100 on the rollover study, the first dose of IMCgp100 (RC1D1) must be administered with overnight inpatient monitoring.

Patients experiencing a grade 3 or 4 hypotension event during any dose of IMCgp100 will require inpatient hospitalization for the next 2 doses. Further inpatient hospitalizations are at the discretion of the investigator.

Patients receiving IMCgp100 as an outpatient, for whom no grade 3 or 4 hypotension event was observed, should be monitored in the clinic for a minimum of 1 hour after the IMCgp100 infusion with at least 2 post-dose vital signs measurements performed.

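### Grade 3 or 4 hypotension during an infusion can be recorded under more than one Table 6-2 row, with incompatible instructions on further dosing and no visible rule for choosing between them

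*Protocol*

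**What the plan says.** Table 6-2 of the protocol has separate blocks for infusion reactions, hypotension and CRS.

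- **Infusion reactions, Grade 3 or 4:** "Discontinue infusion immediately, and permanently discontinue patient from study treatment". The supportive care listed is: "Provide supplemental oxygen, fluids, and other resuscitative measures as needed". Blood pressure is among the signs to be monitored.
- **Hypotension, Grade 3 or 4:** "Hold all doses of IMCgp100 until returned to NCI CTCAE grade" 1 or lower. The row does not mention permanent discontinuation and makes no exception for onset during an infusion.
- **CRS, Grade 3 and Grade 4:** stop the infusion. If symptoms settle to Grade 1 within 7 days, restart may be considered once the Medical Monitor has agreed in writing.

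Section 7.3.2 adds: "Patients experiencing a grade 3 or 4 hypotension event during any dose of IMCgp100 will require inpatient hospitalization for the next 2 doses". It continues: "Further inpatient hospitalizations are at the discretion of the investigator". Section 6.6, on treatment discontinuation, includes CRS of Grade 3 or higher in its definition of unacceptable toxicity.

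At Grade 2, the infusion-reaction row says: "If the adverse event recurs at the reinitiated slow rate of infusion, and despite oral pre-medication, then permanently discontinue the patient from study treatment". The Grade 2 CRS row says: "If recurs with restarting infusion, hold the dose of IMCgp100 and institute supportive measures as indicated".

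Section 6.2.2 advises care with anti-hypertensives "because transient hypotension has previously occurred during infusions of IMCgp100 and monoclonal antibodies". The sentence then runs into redacted text.

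**The concern.** The protocol treats hypotension during an infusion as a known event with this drug. If such an event is severe, one site may record it as an infusion reaction, another as hypotension and a third as part of CRS. Each site can point to a Table 6-2 row that supports what it does, but the rows differ on whether the patient may be dosed again.

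The main stake is patient safety. Re-exposure after a severe event could depend on the recorded term and not on what happened to the patient. The second stake is the data. Safety is the primary objective and tolerability is a secondary endpoint, so a discontinuation that depends on labelling makes those descriptive summaries harder to interpret.

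**Working it through.** No arithmetic applies: the protocol has no formal sample size and the SAP plans no hypothesis tests. The check sets the texts side by side and looks for a rule that ranks them.

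**Step 1. What each label leads to at Grade 3 or 4.**

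| Recorded as | Further dosing | Source |
|---|---|---|
| Infusion reaction | None; permanent discontinuation | Table 6-2 |
| Hypotension | Held until Grade 1 or lower, then at least two inpatient doses foreseen | Table 6-2 and Section 7.3.2 |
| CRS | Restart may be considered with written approval | Table 6-2 |
| CRS | Listed as a reason to discontinue | Section 6.6 |

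The first two rows are incompatible: Section 7.3.2 cannot be applied to a patient who has been permanently discontinued. The last two rows are in tension whatever label is chosen.

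**Step 2. Whether one event can fit more than one row.** The infusion-reaction row neither names nor excludes hypotension, and the visible text does not define an infusion reaction. That row calls for fluids, resuscitative measures and blood-pressure monitoring. Section 6.2.2 places hypotension during infusions. Sections 3.2 and 7.1 cite severe infusion-related toxicity and hypotension together as grounds for overnight monitoring. The CRS rows include intravenous fluid support. Overlap is therefore foreseeable, but it is an inference.

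**Step 3. Whether any rule chooses between rows.** Three candidates appear in the visible text, and none does so.

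- The sentence after Table 6-2 bases modifications on the worst earlier toxicity. Where the competing rows cover the same grades, this does not rank them.
- The precedence statement in Section 6.5 puts institutional protocols for immune-related events above the table. It does not order rows within it.
- The block for other adverse events applies only to events outside the specific criteria.

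**Step 4. Grade 2 recurrence.** An event that fits both the infusion-reaction and CRS rows and recurs on restart leads to permanent discontinuation under one and a hold under the other. The stated conditions differ: the reduced rate and oral pre-medication appear only in the infusion-reaction row.

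**Step 5. What reaches the analysis.**

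- SAP Section 15.1.2 flags an event as leading to discontinuation from the recorded action taken with study drug, so this flag can follow the label.
- SAP Section 13.1 counts a dose interruption only when an entire dosing visit is missed and dosing later restarts. An infusion restarted the same day does not count. Nor does an event that resolves before the next weekly visit if that dose is given.
- The event is an adverse event under any label, so the primary incidence does not change.

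**The case against.** The strongest reply is that the protocol already covers the case. Hypotension has its own row, Section 7.3.2 addresses Grade 3 or 4 hypotension during any dose, and the two agree. On ordinary reading, the row that names the event governs it. Sections 3.2 and 7.1 can also be read as listing two distinct risks, which would explain separate rows.

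This stands as a coherent reading for isolated hypotension. However, the visible text does not state it, and it does not settle hypotension that is part of an infusion reaction or CRS.

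Three further points have weight.

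- Text is redacted in Section 6.1, after Table 6-1, and in Section 6.2.2, directly after the remark on hypotension. A governing rule could sit there. This limits confidence.
- The table's title and Section 6.5 present its contents as recommendations and guidelines. That softens the conflict without removing it, because the infusion-reaction row is worded as an instruction and Section 7.3.2 as a requirement.
- Section 6.6 lets the investigator or sponsor stop treatment for any adverse event judged to contraindicate further dosing. A patient managed under the hypotension row will therefore not necessarily continue.

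A reader might infer that every Grade 3 or 4 hypotension event during an infusion is affected, or every Grade 2 event that recurs. The documents do not support that: the conflict arises only where an event fits more than one row. Nor are all such events life-threatening; the SAP classes Grade 3 as severe and reserves life-threatening for Grade 4.

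**Conclusion.** The point holds in a limited form. For severe hypotension during an infusion that fits more than one Table 6-2 row, the protocol gives incompatible instructions on further dosing and no visible rule for choosing. Section 6.6 adds a tension with the CRS rows that does not depend on labelling. A narrower version exists at Grade 2.

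The size cannot be put in numbers, because the frequency of such events is not given. For an affected patient, re-exposure and the discontinuation flag can depend on the site's choice of term.

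A reader might also infer that each re-dosed event would be counted as a dose interruption, or that the primary endpoint is distorted. Neither follows: an interruption requires a whole missed dosing visit followed by restart, and the adverse event is counted under any label.

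The conclusion assumes that infusion-time hypotension can qualify as part of an infusion reaction or CRS, and that the redacted text contains no governing rule. Confidence is medium.

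**What to change.** Reconcile the infusion-reaction, hypotension and CRS rows of Table 6-2 with Sections 6.6 and 7.3.2. Section 6.6 must be included; otherwise its conflict with the CRS rows would remain after the amendment. Add one sentence to Section 6.5 stating which row governs when an infusion-time event meets more than one, including hypotension that is part of an infusion reaction or CRS and a Grade 2 event that recurs on restart. Then make whatever conforming edits Sections 6.6 and 7.3.2 need. If the redacted text already settles the matter, a cross-reference from Section 6.5 may suffice for the choice of row.

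The sponsor must decide which action applies; this review takes no position on that. The cost is one sentence and conforming edits in a protocol amendment, with no added procedures or patients.

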**Table 6-2 Recommended Dose Modifications by Toxicity Grade for Study Medications**

Worst Toxicity NCI CTCAE v4.03 Grade	Recommended Dose Modifications
Grade 2	Intravenous fluid support and other supportive measures for additional AE as needed.
Grade 3 or 4	Hold all doses of IMCgp100 until returned to NCI CTCAE grade $\leq$ 1. Intravenous fluid support and other supportive measures for additional adverse events. In cases of hypotension where fluid support is not adequate, consider systemic corticosteroid therapy as needed for hypotension. In case of hypotension not responding to intravenous corticosteroid, inotropic pressor support may be indicated.
Cytokine Release Syndrome	
Grade 2	Interrupt infusion of IMCgp100. Supportive measures for symptoms of cytokine release, ie, intravenous fluid support, non-steroidal anti-inflammatory drug (NSAID), antihistamine. If resolves within 4 hours, may restart infusion of IMCgp100. If recurs with restarting infusion, hold the dose of IMCgp100 and institute supportive measures as indicated.
Grade 3	Discontinue infusion immediately. Supportive measures for symptoms of cytokine release, ie, intravenous fluid support, NSAID, antihistamine. To consider intravenous corticosteroid (eg, methylprednisolone or hydrocortisone) for severe symptoms and management of sequelae. If symptoms resolve to NCI CTCAE grade 1 within 7 days, may consider restarting IMCgp100 after written approval of Sponsor Medical Monitor.
Grade 4	Discontinue infusion immediately. Supportive measures for symptoms of cytokine release. In addition to supportive measures, intravenous corticosteroid dosing (eg, methylprednisolone or hydrocortisone) should be administered. If symptoms do not resolve with intravenous corticosteroid dosing consider anti-IL6 (tocilizumab) therapy. If symptoms resolve to NCI CTCAE grade 1 within 7 days, may consider restarting IMCgp100 after written approval of Sponsor Medical Monitor.
Other Adverse Events	
In patients experiencing adverse events (not meeting the specific criteria above) of grade $\geq$ 3, study drugs should be omitted until resolved to grade $\leq$ 1. Treat according to institutional practice and for immune-related adverse events of grade 3 or greater, treatment with corticosteroids should be considered. Consult Sponsor Medical Monitor for further guidance as needed.	

NCI CTCAE = National Cancer Institute Common Terminology Criteria for Adverse Events; NSAID = non-steroidal anti-inflammatory drug.

All dose modifications should be based on the worst preceding toxicity. Once a dose has been reduced it will not be increased at a later time even if there is no toxicity. Patients who require more than 2 dose reductions should discontinue treatment.

